A multidisciplinary intervention in total knee arthroplasty - a multicenter, randomized controlled trial in osteoarthritis patients (MULTI-KNEE trial).

This is a protocol for a multicenter, three-armed, randomized controlled trial (RCT). An estimated one in five patients undergoing total knee arthroplasty (TKA) does not improve in pain and function, suggesting that among the 6466 patients who underwent primary TKA in Norway in 2016, more than 1200 patients derived little or no benefit from the surgery and continue to experience chronic pain. In addition, these numbers suggest that more than 100 000 000 NOK are spent every year on an invasive treatment with questionable effect⁽¹⁾. This study will evaluate the effect of a multidisciplinary intervention delivered either as a substitute, or in addition to, TKA for patients identified as being at risk for non-improvement after TKA.

Hypotheses, aims and objectives

The overall aim of this study is to test the effectiveness of a 12-week integrated Physiotherapy (PT) group exercise program in combination with cognitive behavioral therapy (CBT) support, delivered by physiotherapists, in patients with knee osteoarthritis (OA) who are on a waiting list for TKA and who are identified as being at risk for non-improvement based on a set of preoperative criteria. The effects of the integrated PT exercise program and CBT will be evaluated both as a substitute for TKA and as a supplement to TKA in comparison to TKA alone. We hypothesize that for patients identified as being at risk for postoperative non-improvement: 1) the effect of PT exercise and CBT alone will be equivalent to surgical treatment alone, and 2) the effect of PT exercise and CBT in combination with surgical treatment will be better than surgical treatment alone. The effects of the three treatments will be evaluated in terms of pain relief (primary outcome), functioning and quality of life (QOL) (secondary outcomes) at 12-month follow-up. The study includes a pilot study with 15 participants prior to the full-scale study.

This large study consists of four sub-studies and a pilot study, each with individual aims.

The pilot study has the following aims:

- To evaluate the feasibility of the multidisciplinary intervention alone and as a supplement to TKA
- To evaluate the rate of recruitment, patients' willingness to participate and adherence to the intervention
- Investigate patients' experiences with participation in the study

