Sub-study 1 has the following aims:

- 1a) Investigate the effectiveness of the multidisciplinary intervention alone and as a supplement to TKA in comparison with TKA alone, on pain measured by the Knee Injury and OA Outcome Score (KOOS) at 1-year follow-up (primary outcome)
- 1b) Investigate the effectiveness of the multidisciplinary intervention alone and as a supplement to TKA on the KOOS subscores function and stiffness
- 1c) Evaluate adverse events in the three study arms during the first year following randomization

Sub-study 2 has the following aims:

- 2a) Evaluate the adherence and feasibility of the multidisciplinary intervention in a feasibility study
- 2b) Determine the effects of the multidisciplinary intervention, on lower extremity strength and range of motion at 12 months follow-up
- 2c) Investigate the effects of the multidisciplinary intervention on health-related quality of life at 12 months follow-up

Sub-study 3 has the following aims:

- 3a) Investigate the cost-effectiveness of the multidisciplinary intervention alone and as a supplement to TKA, in comparison with TKA alone
- 3b) Assess the use of health care resources at 2-year follow-up in the 3 treatment arms
- 3c) Assess the use of medication at 2-year follow-up in the 3 treatment arms

Sub-study 4 has the following aims:

- 4a) Compare the effect in the 3 treatment arms on sports and recreation, walking and physical performance 2 years following the intervention
- 4b) Investigate the longitudinal relationship between pain catastrophizing, fear of movement and depression, on functional levels in the 3 treatment arms during the 2 years following the intervention
- 4c) Identify barriers to and benefits of increased adherence to physical activity in patients with painful knee OA

Methods/Design

This is a multicenter randomized controlled trial with three arms: 1) PT + CBT intervention alone, 2) PT + CBT in combination with TKA, and 3) standard care control group receiving TKA. The protocol adheres to the CONSORT guidelines and to the principles of the Declaration of Helsinki, and is approved by the The Regional Medical Research Ethics committee of Health East of Norway (2017/968).

Project arrangements, method selection and analyses

Intervention

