Adverse events	Patients, physiotherapists, medical records	0, 3, 6, 12 and 24 months
Recruitment, screening, randomization	Flow chart, inclusion and exclusion	0, 3, 6, 12 and 24 months
Retention in study/loss to follow-up	Loss to follow-up, crossover	0, 3, 6, 12 and 24 months

Registry-based data

Use of health care resources: registry data from the KUHR-system (i.e., control and payment of reimbursements to health service providers), the Norwegian Patient Registry (NPR) and FD Trygd social security database. All information will be anonymized and linked to each patient using a unique ID number generated prior the start of this study. Data on revision surgery and deep prosthetic infections will be retrieved from the Norwegian Arthroplasty Registry⁽²⁶⁾.

Other measures

Adherence with AktivA: The physiotherapists will monitor patients' adherence with the AktivA program during the 12 weeks. Adherence will be measured as the total number of the 24 sessions completed. Good compliance will be defined as participation in 75% or more of the exercise sessions, medium compliance will be defined as participation in 50-74% of the sessions, and poor compliance will be defined as participation in less than 50% of the sessions.

Compliance with the e-therapy program: Good adherence to the e-therapy program will be defined as completing 75% of the content; medium compliance will be defined as completing 50-74% of the program, and poor compliance will be defined as completing less than 50% of the sessions. In addition, time used in the program will be assessed.

Power calculation and sample size

The primary outcome measure is KOOS pain subscale, 12-month follow-up. The minimal perceptible clinical improvement (MPCI) for KOOS has been determined to be 10 points⁽¹³⁾ which will be considered a minimal clinically important change. The power will be set to 80%, the level of significance at 1%, and the standard deviation of the measurements considered equal in both groups at 16, resulting in a sample size of 62 patients in each treatment group. The attrition rate will be set to 20% to account for drop-out and crossovers. Therefore, we will include and randomize a total of 230 patients.

Statistical analysis

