Data analyses will be performed using SPSS version 24.0 (IBM, Armonk, NY) and STATA version 14.2. Differences between the intervention and control group will be analyzed using responder analysis based on the OMERACT-OARSI responder criteria^(27, 28). Differences between the intervention and control groups at 12 months will also be analyzed using ANOVA. Non-normally distributed data will be analysed using the Kruskal-Wallis test. Differences over time at 3, 6 and 12 months will be analysed using mixed models for repeated measures to account for dependencies caused by each patient being measured several times. P-values <0.05 will be considered statistically significant, and all estimates will be reported with 95% confidence intervals. Effect sizes will be calculated for group differences using Cohen's coefficient *d*. A *d*-value ≥ 0.40 will be considered a clinically meaningful difference⁽²⁹⁾. All analyses will be performed based on the intention to treat principle.

Economic evaluation

The cost-effectiveness analysis will be based on the Norwegian healthcare system. A societal perspective will be used as recommended by Russel et al⁶⁷. A Markov decision model will form the theoretical framework for a cost-effectiveness analysis to estimate the costs and benefits for patients in the two intervention groups and the control group. With this model, simulation will be performed of long-term health benefits, health care costs and cost-effectiveness of the specified interventions. The main variables will be QALYs based on the EQ5D, combined with use of health care resources and use of medication. The incremental cost-effectiveness ratio (ICER) will be used to summarize the cost-effectiveness of each of the intervention groups, compared to the control group. Sensitivity analyses will be performed to test the stability of the conclusions. According to the literature, a clinically relevant difference in EQ5D between the groups would be 0.08⁶⁸. Keeping alpha to 5% and power to 80%, we would need 42 individuals in each group.

Given we plan to enroll 62 in each group, our study is sufficiently powered to reveal a clinical relevant difference also for this secondary aim.

Timelines

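### The three-group test named for 12-month differences does not match the two comparisons with TKA alone that the hypotheses and the sample size are built on

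*Protocol*

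**What the plan says.** The protocol describes the design thus: "This is a multicenter randomized controlled trial with three arms". The arms are PT+CBT alone (arm 1), PT+CBT with TKA (arm 2) and TKA alone (arm 3).

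- **Hypotheses, aims and objectives** states two claims. Hypothesis 1 claims equivalence of arm 1 and arm 3. Hypothesis 2 claims superiority of arm 2 over arm 3: "the effect of PT exercise and CBT in combination with surgical treatment will be better than surgical treatment alone".
- **Sub-study 1, aim 1a**, which carries the primary outcome, keeps the same comparator: "Investigate the effectiveness of the multidisciplinary intervention alone and as a supplement to TKA in comparison with TKA alone".
- **Power calculation and sample size** takes a 10-point difference, 80% power, a 1% level and "the standard deviation of the measurements considered equal in both groups at 16". It arrives at 62 per arm.
- **Statistical analysis** says "Differences between the intervention and control groups at 12 months will also be analyzed using ANOVA". For data that are not normal it adds: "Non-normally distributed data will be analysed using the Kruskal-Wallis test". The threshold is P<0.05.

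The Statistical analysis section also lists an OMERACT-OARSI responder analysis (worded as if there were a single intervention group), mixed models over 3, 6 and 12 months, 95% confidence intervals for all estimates, and Cohen's d for group differences. It names no pair of arms for any of these, and no equivalence test.

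**The concern.** On three arms, ANOVA and Kruskal-Wallis have two degrees of freedom, no direction, and the null hypothesis that all three arms are alike. That null includes PT+CBT alone versus add-on, which is neither a stated hypothesis nor part of aim 1a. A significant result does not say which arms differ or in which direction, so by itself it cannot support the superiority claim. Neither result can support the equivalence claim: a significant P does not locate the difference, and a non-significant P does not demonstrate equivalence.

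At stake is whether the 12-month KOOS pain result, as the protocol words it, answers the trial's own two questions. Two analysts following the text could report different main results, one the overall P and the other a pair chosen afterwards.

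**Working it through.** **Inputs.** From Power calculation and sample size: difference 10, SD 16, level 1%, power 80%, n = 62 per arm. From Statistical analysis: level 5%. Assumed here: 62 analysed per arm, normal data, equal variances. True means are written as (arm 1, arm 2) relative to TKA alone.

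**Step 1: the plan's own figure.** Two-group normal formula, two-sided 1%: n = 2 × 16² × (2.576 + 0.842)² / 10² = 59.8, so 60. The exact two-sample t-test gives 62 (power 0.804; 0.796 at n = 61). The stated 62 is therefore reproduced as a two-group contrast.

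**Step 2: power of the overall test.** Noncentral F on (2, 183) degrees of freedom, λ = n × Σ(μᵢ − μ̄)² / SD².

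| True means vs TKA | λ | Power at 5% | Power at 1% |
|---|---|---|---|
| (0, +10): both hypotheses true | 62 × 66.67/256 = 16.1 | 0.955 | 0.860 |
| (−10, 0): 10-point deficit, no add-on benefit | 62 × 66.67/256 = 16.1 | 0.955 | 0.860 |
| (−5, +5) | 62 × 50/256 = 12.1 | 0.881 | 0.712 |

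The first two rows are opposite answers to the trial's questions, and the overall test cannot tell them apart.

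**Step 3: the overall test beside the contrasts.** The standard error of a pairwise difference is 16 × √(2/62) = 2.874. Simulated trials with pooled-variance contrasts at 5%:

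| True means | Overall | Arm 1 vs 3 | Arm 2 vs 3 | Arm 1 vs 2 | Overall rejects, neither TKA contrast does |
|---|---|---|---|---|---|
| (−5, +5) | 88% | 41% | 41% | 93% | 16 to 17% |
| (0, +10) | 96% | 5% | 93% | 93% | about 3% |
| (−10, 0) | 96% | 93% | 5% | 93% | about 3% |

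At 1%, the (−5, +5) row has the overall test at 71%, add-on versus TKA at 20%, and the last column at 33%. Kruskal-Wallis behaves like ANOVA: 0.87 at 5% for (−5, +5).

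**Step 4: one worked result.** Suppose the observed differences from TKA are −5 and +5 with SD 16. Then F = 62 × 25/256 = 6.05, p = 0.003. Each comparison with TKA has t = 5/2.874 = 1.74, p = 0.084. PT+CBT alone versus add-on has t = 10/2.874 = 3.48, p = 0.0006. The overall test is clearly significant, and the only pair significant at 5% is the one outside the stated hypotheses.

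**Step 5: hypothesis 1.** Equivalence needs a margin m, and the protocol gives none. For a true difference of 0, the power of two one-sided tests is about 2Φ(m/2.874 − z) − 1. For assumed margins of 10, 8 and 5 points this is 0.93, 0.75 and 0.08 at one-sided 5%. With a 95% interval (one-sided 2.5%) it is 0.87, 0.59 and 0.

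**The case against.** The best defence is that the text never says the conclusion rests on the overall F test. It speaks of differences from control, ANOVA is also a model from which contrasts are drawn, and choosing contrasts is commonly left to a SAP, which is not at hand. Confidence intervals and Cohen's d cannot come from a two-degree-of-freedom test, so pairwise estimates are implied. An overall test followed by pairwise tests is a recognised safeguard with three groups. At the planned effect it costs little: both the overall test and the add-on contrast are significant in about 92% of trials, against 93% for the contrast alone.

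Much of this stands, and it rules out several stronger readings that a reader might infer:

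- *The overall P is the primary decision rule.* The section labels no test as primary, and ANOVA is introduced second, after the responder analysis.
- *Only all-arms-equal tests are planned.* The responder analysis, mixed models, intervals and effect sizes are also there.
- *The 96% rejection at (−10, 0) is a false positive.* It is not. PT+CBT alone truly differs from TKA by 10 points, that contrast is itself significant in 93% of trials, and the overall test rejects without either TKA contrast in only about 3%.
- *Arm 1 versus arm 2 is foreign to the trial.* The two hypotheses together imply that these arms differ, although neither states it.

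What the defence does not remove is that the protocol names a test that does not match its stated questions. Kruskal-Wallis beside ANOVA points to a three-group comparison, no follow-up sequence is given, and no pair is attached to the intervals or effect sizes. A gate of this kind would not serve the equivalence claim in any case.

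**Conclusion.** The mismatch holds and is worth correcting, as a should-fix. The hypotheses and aim 1a fix two comparisons with TKA alone, and the sample size reproduces as a two-group contrast, but the 12-month test named is a three-group one. By itself it answers neither hypothesis, which the identical power of 0.955 under opposite truths shows most plainly.

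The 16 to 17% of trials in which the overall test rejects without either TKA contrast belongs to one symmetric scenario (−5, +5), chosen for illustration. In the 10-point scenarios it is about 3%. The figures assume 62 analysed per arm, SD 16 and normal data. That the test is an overall one is inferred from naming ANOVA and Kruskal-Wallis for three arms. The 1% level used for sizing against the 5% level used for analysis is a separate inconsistency, and this point does not depend on it.

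**What to change.** In the Statistical analysis section, name two main comparisons for KOOS pain at 12 months, both from one three-arm model and each with an estimate and confidence interval:

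1. Arm 2 minus arm 3, tested for superiority (hypothesis 2).
2. Arm 1 minus arm 3, with its confidence interval judged against a pre-stated equivalence margin (hypothesis 1), not by a non-significant P.

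Make arm 1 versus arm 2 secondary, and say that the overall P-value alone does not decide either hypothesis. State which pairs the confidence intervals and Cohen's d refer to. Reconcile the 1% and 5% levels separately, since that choice sets the width of the intervals.

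The cost is analysis wording plus stating a margin, with no new data. The margin does need thought: as shown in the working, 62 per arm gives reasonable equivalence power for an assumed margin of 10 points and almost none for 5.

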The PT component of the intervention will be based on the evidence-based AktivA program, which is the Norwegian equivalent of Sweden's Better Living with OsteoArthritis (BOA)⁽²⁾ and Denmark's Good Life with OsteoArthritis (GLA;D) programs⁽³⁾, developed specifically for hip and knee OA. The GLA;D program reduced pain in patients with hip and knee OA and the results were sustained for 12 months⁽³⁾.

The CBT component of the intervention will be delivered as an e-therapy program using text combined with animated videos. The e-learning program is currently under development for this study in close cooperation with Braive A/S and will be based on Linton's standardized CBT intervention program for pain-related disability and pain chronicity⁽⁴⁾, modified for OA patients⁽⁵⁾.

Physiotherapist certification: PTs who will deliver the intervention will participate in a full day interdisciplinary certification course delivered by an orthopedic surgeon, PTs, a nutritionist, and a patient with OA to provide a user perspective. Upon completion, the PTs will be certified AktivA providers.

All physiotherapists will also participate in a CBT education program led by a psychologist. The goal is to enable the PTs to be mentors for the participants' progress in their e-learning program, monitor the patients' progression and help the patients to integrate their new skills into their physical activity program. A manual will be developed and made available for the physiotherapists. The psychologist will then serve as a consultant to the physiotherapists.

The intervention will consist of the following elements (See Figure 1):

- Group OA education (a theoretical patient education program).
- Exercise therapy program consisting of a physical activity program with integration of CBT skills⁽⁶⁾. This part of the intervention is led by an AktivA certified PT who is also trained to support and integrate the CBT e-therapy program.
- CBT e-therapy program that consists of 12 modules focused on training in a number of pain coping skills. Participants complete this part of the intervention at home and at their own pace.

[figure not shown]
Figure 1 – overview of the components of the intervention.

Recruitment and allocation

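### Exercise is given in physiotherapist-led groups in two of the three arms, but the named analyses and the sample size make no allowance for correlation within groups or therapists

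*Protocol*

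**What the plan says.** The overall aim (Protocol, Hypotheses, aims and objectives) describes the intervention as a "12-week integrated Physiotherapy (PT) group exercise program in combination with cognitive behavioral therapy (CBT) support, delivered by physiotherapists". The Intervention section adds an OA education component, also given to groups. Of the exercise component it says: "This part of the intervention is led by an AktivA certified PT who is also trained to support and integrate the CBT e-therapy program". The CBT modules themselves are individual: "Participants complete this part of the intervention at home and at their own pace".

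Methods/Design lists the arms as "1) PT + CBT intervention alone, 2) PT + CBT in combination with TKA, and 3) standard care control group receiving TKA". The groups therefore exist in arms 1 and 2 only, and both hypotheses compare one of these arms with TKA alone.

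The Statistical analysis section names a responder analysis, ANOVA at 12 months with Kruskal-Wallis for non-normal data, and, for change over 3, 6 and 12 months, "mixed models for repeated measures to account for dependencies caused by each patient being measured several times". It sets significance at 0.05 with 95% confidence intervals. The Power calculation section takes a 10-point difference, SD 16, 80% power and a 1% level, "resulting in a sample size of 62 patients in each treatment group". The protocol mentions no correlation by exercise group or physiotherapist, no ICC and no design effect.

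**The concern.** Patients who train together for 12 weeks under one physiotherapist, who also supports their CBT, may have outcomes more alike than patients in different groups. In arms 1 and 2 such patients carry less independent information than their number suggests. In arm 3 there is no corresponding group. This is a partially nested design, and each hypothesis compares a nested arm with an un-nested one.

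The point bears most directly on the ANOVA at 12 months, the primary time point, because ANOVA models no dependency at all. The mixed model handles repeated measurements within a patient, which is a different dependency. With any positive correlation within groups or therapists, both analyses understate the standard error of PT versus TKA. The reported 95% intervals would then cover less than 95%, and a difference such as superiority of arm 2 over arm 3 would be declared too often when none exists.

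**Working it through.** **Inputs from the protocol.** Difference 10, SD 16, level 1% and power 80% (Power calculation and sample size); level 5% (Statistical analysis); 62 evaluable patients per arm.

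**Assumed, because the protocol does not give them.** m = 4 to 12 patients of an arm sharing a group or therapist, and ICC = 0.01 to 0.10. Total SD is 16 in every arm, clusters are of equal size, and the normal approximation is used.

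**1. Reproduce the stated sample size.** With independent patients and a two-sided test, n = 2 × [16 × (2.576 + 0.842)/10]² = 59.8, so 60 per arm. The noncentral-t calculation gives power 0.796 at 61 and 0.804 at 62, so the stated 62 is recovered exactly. No clustering allowance is contained in it. For the total, 3 × 62/0.8 = 232.5, close to the stated 230.

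**2. Standard error without clustering.** SE₀ = 16 × √(2/62) = 2.874.

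**3. Standard error with clustering in the PT arm only.** The design effect is DE = 1 + (m − 1) × ICC, and SE = 16 × √[(1 + DE)/62]. The ratio SE/SE₀ is √[(1 + DE)/2].
- m = 4, ICC 0.01: DE = 1.03, ratio √1.015 = 1.007
- m = 8, ICC 0.05: DE = 1.35, ratio √1.175 = 1.084
- m = 12, ICC 0.10: DE = 2.10, ratio √1.55 = 1.245

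**4. Type I error and power.** True type I error = 2 × [1 − Φ(z/ratio)], with z = 1.960 at 5% and 2.576 at 1%. Power = Φ(10/SE − z). Coverage of a nominal 95% interval is one minus the type I error at nominal 5%.

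| Scenario | SE ratio | Type I, nominal 5% | Coverage of 95% CI | Type I, nominal 1% | Power at 1% | Power at 5% |
|---|---|---|---|---|---|---|
| Independent | 1.000 | 5.0% | 95.0% | 1.0% | 82% | 94% |
| m = 4, ICC 0.01 | 1.007 | 5.2% | 94.8% | 1.1% | 81% | 93% |
| m = 8, ICC 0.05 | 1.084 | 7.1% | 92.9% | 1.8% | 74% | 89% |
| m = 12, ICC 0.10 | 1.245 | 11.5% | 88.5% | 3.9% | 59% | 80% |

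Worked line for the middle scenario: 1.960/1.084 = 1.808, giving 7.1%. SE = 2.874 × 1.084 = 3.115 and 10/3.115 = 3.210. Power is then Φ(3.210 − 2.576) = 74% at 1% and Φ(3.210 − 1.960) = 89% at 5%.

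**5. Number of clusters.** 62/8 is about 8 groups per PT arm and 62/12 about 5. With so few, the degrees of freedom need a small-sample correction.

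**The case against.** The strongest reply is that random-effects structure is ordinarily settled in the SAP, which is not shown, and that the mixed-model sentence gives one reason for the model without calling it the only dependency. That is fair as far as it goes. But the protocol does more than stay silent: it names tests for the primary time point that assume independent patients, and it sizes the trial on independence. A SAP that added a group term would have to depart from the named ANOVA, and the stated power would still need revising.

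The second reply is that the size is unknown. The number of therapists is not given, nor whether groups are closed or rolling. The CBT modules are done alone at home, and the outcome is read long after a 12-week programme ends. All of this stands. At ICC 0.01 with groups of 4 the effect is negligible, so the point must be stated conditionally.

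Three stronger readings are tempting but not supported:
- **Arm 1 versus arm 2 is affected even more.** This requires the two arms to train in separate groups, which the protocol does not say. If they share groups, positive correlation would make that test conservative. Neither hypothesis makes this comparison.
- **Equivalence of arm 1 and TKA becomes too easy to claim.** This presumes an equivalence test based on a confidence interval. The protocol gives no margin and no such test. If equivalence were read from a non-significant difference, an understated standard error would make the claim harder.
- **The trial is underpowered.** Power falls clearly only at the 1% level used for sizing. At the 5% level of the analysis it stays at about 80% or above over the whole assumed range.

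**Conclusion.** The point holds in conditional form. The design creates groups in two arms, while the named 12-month tests, the stated purpose of the mixed model and the sample size all leave them out. If outcomes correlate within exercise groups or therapists, standard errors for each PT arm versus TKA will be too small. Over the assumed range the understatement runs from trivial to material, and the protocol does not allow it to be narrowed. The consequence is mainly for type I error and interval coverage, much less for power at the level at which results will be judged. It would be wrong to infer that the standard errors are certainly too small, since that needs a positive ICC which the documents neither give nor exclude.

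**What to change.** - Record exercise-group and physiotherapist identifiers for every patient in arms 1 and 2. Physiotherapists already log attendance (Other measures), so the link should be easy to obtain.
- Analyse 12-month KOOS pain with a partially nested mixed model in place of the plain ANOVA: a random intercept for group or therapist in arms 1 and 2 only, each arm 3 patient as a separate unit, and Satterthwaite or Kenward-Roger degrees of freedom. Add the same term to the repeated-measures model.
- Restate the power with the assumed group size and ICC, at the level used in the analysis.
- Make no statement about the effect of clustering on equivalence unless a confidence-interval equivalence test is specified.

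The cost is one or two data fields, a changed model statement, slightly wider confidence intervals and a lower stated power at the 1% level (74% in the middle scenario). No extra patients are proposed. Restoring 80% at the 1% level would take about 61, 71 or 93 evaluable patients per arm in the three scenarios (normal approximation, against 60 without clustering), but power at the 5% level does not call for that.

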The primary outcome will be the pain subscore from the KOOS at 12 months. The KOOS is a knee joint specific questionnaire developed in 1998 for the purpose of evaluating short-term and long-term symptoms and functioning in subjects with knee injury and OA. KOOS is a 42-item survey designed to assess people's opinions about the difficulties they experience with activity due to problems with their knees during the past week. Each of the 42 items carries equal weighting (0–4), with higher scores indicating better outcomes. KOOS has 5 subscales: pain, other symptoms, activities of daily living (ADL), function in sport and recreation, and knee-related QOL. Scores are transformed to a 0-100 scale, with 0 representing extreme knee problems and 100 representing no problems. The KOOS has been validated for use in TKA and has been shown to be a valid, reliable and responsive measure⁽¹³⁾.

Secondary outcomes will include the 4 remaining KOOS subscales and the following additional measures:

Patient-reported outcomes

Pain intensity and interference with functioning: the Brief Pain Inventory⁽¹⁴⁾.

Sleep quality: the Pittsburgh Sleep Quality Index (PSQI)⁽¹⁵⁾.

Pain Catastrophizing: the Pain Catastrophizing Scale (PCS)⁽¹⁶⁾.

Pain-related fear of movement: the Fear-Avoidance Belief Questionnaire (FABQ)⁽¹⁷⁾.

Mood states (depression and anxiety): the Hospital Anxiety and Depression Scale (HADS)⁽¹⁸⁾.

Health-related quality of life (HRQoL): EuroQol-5D-3L (EQ-5D-5L)⁽¹⁹⁾.

The Health Locus of Control Scale (HLCS) will be used to measure patients' anticipations between own health and disease behavior and consequences of the behavior⁽²⁰⁾.

The Forgotten Joint Score will be used to assess how natural the prosthesis feels after TKA⁽²¹⁾.

Anchor measures: Patient acceptable symptom state, treatment failure, global perceived effect.

Clinical assessments

Knee functioning: the new American Knee Society Score (AKSS)⁽²²⁾.

Comorbidity will be measured with the Self-Administered Comorbidity Questionnaire (SCQ-19)⁽²³⁾.

Time in activity, number of steps: ActivePal Professional single-axis accelerometer⁽²⁴⁾.

Functional lower extremity strength: the 30-second sit to stand test⁽²⁵⁾.

Walking speed will be measured using the 6 minutes walk test.

Radiological assessments

X-rays including weightbearing AP, lateral view, Rosenberg view and long leg weightbearing AP view (HKA), preoperative and at 24 months. OA grading according to Kellgren-Lawrence and Ahlbachs⁽⁴³⁾.

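### Two unranked primary comparisons with TKA alone are judged at 0.05 each, although the trial was sized at 1%, so the chance of a false primary claim is about 7% to 9%

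*Protocol*

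**What the plan says.** Under the hypotheses heading, the protocol evaluates the intervention "both as a substitute for TKA and as a supplement to TKA in comparison to TKA alone". The first hypothesis is that "the effect of PT exercise and CBT alone will be equivalent to surgical treatment alone". The second is that "the effect of PT exercise and CBT in combination with surgical treatment will be better than surgical treatment alone". Neither is ranked above the other. Both are judged on pain relief, and the primary outcome section fixes the endpoint: "The primary outcome will be the pain subscore from the KOOS at 12 months". Aim 1a of sub-study 1 names both comparisons together.

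The power section uses a 10-point difference, SD 16, 80% power and a 1% significance level, "resulting in a sample size of 62 patients in each treatment group". It gives no reason for 1%.

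The statistical analysis section plans a responder analysis, an ANOVA at 12 months (Kruskal-Wallis for non-normal data) and mixed models over time, all described as analyses of differences. It then sets a single rule, "P-values <0.05 will be considered statistically significant", with 95% confidence intervals for all estimates. It does not make the pairwise readings depend on the ANOVA, put them in order, or divide alpha between them.

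**The concern.** Two primary claims rest on one endpoint and one comparator, and each may be made at the full 5% level. The chance that at least one is false then exceeds 5%. The trial was sized at a stricter level, which would have kept that chance low, but the level is not carried into the analysis. So the protocol does not merely leave a detail open: it states two different levels for the same outcome.

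The practical stake is a borderline result. A superiority result for the combination arm with P between 0.025 and 0.05 would be a positive primary finding under the analysis section, but not under the level used for sizing, nor under Bonferroni at 2.5%. Under Holm it would count only if hypothesis 1 had first passed at its stricter level.

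**Working it through.** **Inputs.** From the power section: difference 10, SD 16, alpha 1%, power 80%, 62 per group, 20% attrition, 230 randomized. From the analysis section: alpha 0.05 and 95% intervals. Assumptions: two-sided difference tests; three equal arms, so the two contrasts have correlation 0.5 through the shared control; a 10-point equivalence margin (8 points as a sensitivity case), since the protocol gives none.

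**The plan's own figure.** The two-sample t test at two-sided 1% with 80% power needs 62 per group, with exact power 80.4%. The stated 62 reproduces. One-sided 1% would need only 52 (normal approximation), so the 1% was two-sided. Attrition: 3 × 62 / 0.80 = 232.5, close to the 230 stated; 230 × 0.80 / 3 = 61.3 completers per arm.

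**Two difference tests, both null.** Family-wise error = 1 − P(|Z1| < c and |Z2| < c), with Z1 and Z2 standard normal and correlation 0.5.

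| Level per contrast (two-sided) | c | Family-wise error |
|---|---|---|
| 5% | 1.960 | 9.07% |
| 2.5% | 2.241 | 4.65% |
| 1% | 2.576 | 1.90% |

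Two independent 5% tests would give 1 − 0.95² = 9.75%. If the contrasts were read only after a significant three-group ANOVA at 5%, simulation gives 4.2%, but the protocol states no such gate.

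**Hypothesis 1 as equivalence.** A false claim is now a declaration of equivalence when the true difference lies at the margin. Simulation (62 per arm, SD 16, margin 10, no true effect for hypothesis 2, which is tested at two-sided 5%):

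| How equivalence is read | Any false claim | Only claims favouring the intervention |
|---|---|---|
| Two one-sided tests at 5% (90% interval) | about 9.2% | 6.7% to 7.5% |
| 95% interval inside the margin | about 7.0% | 4.5% to 5.0% |

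The ranges reflect whether the true difference is at the lower or upper margin.

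**Power after a correction, 10-point difference.** Two-sample t test, d = 10/16 = 0.625, 62 per arm: 93.2% at 5%, 88.5% at 2.5%, 80.4% at 1%. With 61 per arm: 92.8%, 88.0% and 79.6%.

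**Power after a correction, equivalence with no true difference.** SE = 16 × √(2/62) = 2.874. Power = 2Φ(margin/SE − z) − 1, with margin/SE = 3.480 for 10 points and 2.784 for 8 points.

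| One-sided level | z | Margin 10 | Margin 8 |
|---|---|---|---|
| 0.05 | 1.645 | 93% | 75% |
| 0.025 | 1.960 | 87% | 59% |
| 0.0125 | 2.241 | 78% | 41% |
| 0.01 | 2.326 | 75% | 35% |

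**The case against.** The strongest objection is that hypothesis 1 is equivalence. A reader might infer that the trial can claim success on whichever contrast crosses 0.05, and that an unusual TKA-alone mean favours both claims at once. The protocol does not support that: for hypothesis 1 a significant difference counts against the hypothesis, and a low TKA-alone mean that helps hypothesis 2 can move hypothesis 1 away from equivalence. This stands. The 9.1% therefore describes two difference tests, and the equivalence reading has to be shown beside it. The excess shrinks but does not vanish, except when equivalence is read from the 95% interval and only errors favouring the intervention are counted (4.5% to 5.0%).

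Second, the analysis section names an ANOVA, and gating the contrasts on it would hold two difference tests near 4.2%. The gate is not stated, and it would not control a false claim of equivalence.

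Third, multiplicity rules are often left to the SAP, which is not at hand. If the protocol were silent, that would settle the matter. It is not silent: it fixes 0.05 for all results after sizing the primary outcome at 1%.

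Fourth, one may hold that separate questions need no adjustment. That is arguable in general. Here the two comparisons share a control arm, an intervention package and one overall aim. Even on that view, the 1% and the 5% still disagree.

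**Conclusion.** The point holds in a limited form. The protocol sizes its primary outcome at 1% and judges it at 5%, with two unranked primary hypotheses against one control arm and no order, gate or split. For the difference tests that the analysis section describes, the family-wise error is about 9.1% rather than the 1.9% implied by the sizing level. With hypothesis 1 tested as equivalence it is about 7.0% to 9.2%, or 4.5% to 7.5% counting only claims favouring the intervention. These figures assume 62 per arm, equal variances, no gate and, for equivalence, a 10-point margin that the protocol does not give.

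A reader might also infer that the planned size absorbs a correction for both hypotheses, with at least 88.5% power each at 2.5%. That figure belongs to the difference test only. For equivalence, power depends on the missing margin and can fall well below 80%.

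**What to change.** Reconcile the power and statistical analysis sections in a few sentences:

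- The two 12-month KOOS pain comparisons with TKA alone form one primary family.
- They are judged at a level stricter than 0.05: either the 1% already used for sizing, or 2.5% each by Bonferroni, or Holm at an overall 5%. Confidence intervals match the level chosen.
- The hypothesis 1 P value comes from an equivalence test against a margin stated in the protocol, not from a difference test. Without a margin, no multiplicity rule can be applied to it.
- PT+CBT alone versus the combination is exploratory.

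No patients are added. For a 10-point difference with 62 per arm, power falls from 93.2% to 88.5% at 2.5%, or to 80.4% at 1%, which is what the sponsor planned for. For hypothesis 1 the cost follows from the margin: with 10 points, power falls from 93% at one-sided 0.05 to 87% at 0.025 and 78% at 0.0125; with 8 points, from 75% to 59% and 41%. The margin should therefore be fixed before the level is chosen.
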